2.3 Benefit/risk assessment

The risk assessment of nanrilefusp alfa is based on nonclinical studies in addition to clinical experience from completed and ongoing trials with nanrilefusp alfa as monotherapy and in combination with pembrolizumab. Clinical safety data from study SC103 (AURELIO-03) in patients with advanced/metastatic solid tumors for nanrilefusp alfa in combination with pembrolizumab showed a similar profile as for nanrilefusp alfa monotherapy; no relevant overlapping toxicities were reported. The majority of treatment-emergent adverse events (TEAEs) were of grade 1 or 2. As of 11Apr2022 (cut-off date for AURELIO-03), the most common TEAEs for nanrilefusp alfa monotherapy / nanrilefusp alfa in combination with pembrolizumab were pyrexia (70.0/81.0%), decreased lymphocyte count (66.7/47.6%), anemia

(60.0/52.4%), injection site reaction (56.7/57.1%), and chills (50.0/61.9%). The most common TEAEs of grade >2 were decreased lymphocyte, anemia, and pyrexia. These TEAEs could be well managed and were self-limiting upon discontinuation of nanrilefusp alfa.

The present combination nanrilefusp alfa/cetuximab study will start with a safety cohort at 9 µg/kg nanrilefusp alfa, which is one dose level below the nanrilefusp alfa RP2D of 12 µg/kg. It is hypothesized that nanrilefusp alfa in combination with cetuximab enhances tumor-directed ADCC and thus improves the clinical outcome in patients with RAS wild-type colorectal cancer.

Preliminary efficacy results in study SC103 (AURELIO-03) in advanced/metastatic solid tumors were encouraging, showing clinical benefit for most patients in the combination part of the study, including patients pretreated with immune checkpoint inhibitors. Maximum activation of natural killer cells was observed already at low dose levels of nanrilefusp alfa, and maximum activation of CD8+ T-cells was reached at 9 to 12 µg/kg nanrilefusp alfa.

More recent information about the known and expected benefits and risks and adverse events (AEs) that could be associated with the administration of nanrilefusp alfa and cetuximab may be found in the Investigator's Brochure (IB) and Erbitux's current package insert/US prescribing information (for the US)¹⁷ and current summary of product characteristics (SmPC; for the EU).¹⁸

In conclusion, the current nonclinical and clinical data on nanrilefusp alfa in patients with advanced/metastatic solid tumors suggest a favorable benefit/risk ratio and justify further clinical development of nanrilefusp alfa.

3 OBJECTIVES AND ENDPOINTS

Objective	Endpoint(s)
Primary	

 To estimate the antitumor efficacy of nanrilkefusp alfa in combination with cetuximab 	
 Objective response rate (ORR) according to Response Evaluation Criteria In Solid Tumors version 1.1 (RECIST 1.1)¹⁹
Secondary	

 To further evaluate the antitumor efficacy of nanrilkefusp alfa in combination with cetuximab 	
 ORR according to RECIST for immune-based therapeutics (iRECIST)²⁰ (iORR) Best overall response according to RECIST 1.1 (BOR) and iRECIST (iBOR) Duration of response according to RECIST 1.1 (DoR) and iRECIST (iDoR) Clinical benefit rate according to RECIST 1.1 (CBR) and iRECIST (iCBR) Progression-free survival (PFS) according to RECIST 1.1 and iRECIST (iPFS) Time to response according to RECIST 1.1 (TtR) and iRECIST (iTtR) Time to progression according to RECIST 1.1 (TtP) and iRECIST (iTtP)

 To assess the safety and tolerability of nanrilkefusp alfa in combination with cetuximab 	
 Type, frequency, and severity of TEAEs according to Common Terminology Criteria for Adverse Events (CTCAE), version 5.0; safety laboratory findings; vital signs; electrocardiography findings

 To determine the RP2D of nanrilkefusp alfa in combination with cetuximab 	
 Dose-limiting toxicities (DLTs)

 To characterize the pharmacokinetics (PK) of nanrilkefusp alfa in a subset of patients 	
 Serum concentrations and calculated PK parameters of nanrilkefusp alfa

Objective	Endpoint(s)

 To determine the immunogenicity of nanrilkefusp alfa in combination with cetuximab 	
 Incidence, titer, and time course of anti-drug antibodies (ADAs) against nanrilkefusp alfa
Exploratory	

 To further evaluate the antitumor efficacy of nanrilkefusp alfa in combination with cetuximab 	
 PFS on next-line anti-cancer treatment (PFS2) Overall survival (OS)

 To determine the status of immune-, molecular-, and disease-related biomarkers of potential importance 	
 Assessment of Fc gamma receptor polymorphism or presence and changes in T-cell clonality, levels of inflammatory/regulatory cytokines or circulating tumor markers such as circulating tumor DNA at screening and following nanrilkefusp alfa and cetuximab treatment

 To determine the impact of the EGFR mutational status on efficacy 	
 Assessment of the EGFR mutational status at baseline and at disease progression

 To characterize the PK of cetuximab in a subset of patients 	
 Serum concentrations and calculated PK parameters of cetuximab

 To determine the immunogenicity of cetuximab in combination with nanrilkefusp alfa 	
 Incidence, titer, and time course of ADAs against cetuximab

4 STUDY DESIGN

4.1 Overall design

Study SC105 (AURELIO-05) is a phase 2, open-label, single-arm, multicenter study with an initial safety run-in with 3+3 safety cohorts. For an overview of the study design please refer to section [1.2](#).

4.1.1 Study design

First, 3 patients will be recruited sequentially so that the first administrations of nanrilkefusp alfa to the first and second patients will be 7 days apart and the second and third patients will not be dosed on the same day. These patients will be treated with cetuximab in combination with 9 µg/kg nanrilkefusp alfa, a dose one dose level below the RP2D as determined in study SC103 (AURELIO-03) which evaluated nanrilkefusp alfa at doses up to 12 µg/kg in combination with pembrolizumab. Please see section [6.1](#) for more details on administration of study interventions.

After the last patient in the 9 µg/kg safety cohort completes the first treatment cycle of 21 days, i.e., the DLT assessment period, an internal safety committee (ISC) will review the safety data.

If at least one patient in the initial 9 µg/kg safety cohort experiences a DLT, an additional 3 patients will be recruited into the 9 µg/kg safety cohort. The ISC will review the safety data of these 3 additional patients and decide whether it is safe to increase the dose to 12 µg/kg nanrilkefusp alfa in combination with cetuximab in the second safety cohort or whether the study should proceed with 9 µg/kg nanrilkefusp alfa or with 6 µg/kg nanrilkefusp alfa.

If there are no safety concerns in the initial 9 µg/kg safety cohort, the study will proceed to the second safety cohort and sequentially recruit another 3 patients who will receive 12 µg/kg nanrilkefusp alfa in combination with cetuximab. As in the 9 µg/kg cohort, the first administrations of nanrilkefusp alfa to the first and second patients will be 7 days apart and the second and third patients will not be dosed on the same day. Safety in the 12 µg/kg cohort will be evaluated by the ISC after the last patient completes the DLT assessment period (first treatment cycle of 21 days).

If at least one patient in the 12 µg/kg safety cohort experiences a DLT, an additional 3 patients will be recruited into the 12 µg/kg safety cohort. The ISC will review the safety data of these 3 additional patients and decide whether it is safe to proceed to the main cohort with patients receiving 12 µg/kg nanrilkefusp alfa in combination with cetuximab or whether the study should continue at a lower nanrilkefusp alfa dose.

If there are no safety concerns in the 12 µg/kg safety cohort, the study will proceed to the main cohort and recruit patients who will receive 12 µg/kg nanrilkefusp alfa in combination with cetuximab.

Patients in the initial 9 µg/kg safety cohort may also have a dose increase to 12 µg/kg nanrilkefusp alfa in the next treatment cycle at the discretion of the investigator if there are no safety concerns in the 12 µg/kg safety cohort.

Patients in the safety cohorts who do not fulfill the DLT evaluability criteria (see section [4.1.3](#)) for any reason other than DLT during the DLT assessment period will be replaced until at least 3 patients per cohort have completed their DLT assessment period.

In the main cohort of the study, patients will be treated with nanrilefusp alfa in combination with cetuximab in 21-day cycles. An independent data monitoring committee (IDMC) will be established to review safety and efficacy data at certain time intervals, or when the interim analysis for futility is triggered, once the main cohort of the study starts.

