4.1.3 DLT evaluability

DLT evaluability is defined as follows:

- Patient completed the first 21-day cycle (DLT assessment period of 21 days)
- Patient received all administrations of nanrilkefusp alfa during the DLT period as per schedule (± 1 day)
- Patient received cetuximab as per schedule (± 1 day)

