6.5 Dose modification and toxicity management

6.5.1 Dose modification and toxicity management for nanrilefusp alfa

Dose modification and toxicity management for nanrilefusp alfa for safety reasons, will be discussed on a case-by-case basis between the site and the sponsor's medical monitor. Recommendations for clinical management of cytokine release syndrome are provided in [Table 6.4](#).

To minimize the risk for injection site reaction, subcutaneous injection sites should be rotated to different areas of the body (upper and lower extremities, each of the 4 quadrants of the abdomen) to minimize the summated local effects of nanrilefusp alfa administration.

To minimize the risks associated with shortening of the QT interval, vital signs and electrocardiography (ECG) must be closely monitored as per Protocol and institutional guidelines.

Liver function tests for nanrilefusp alfa toxicity evaluation in this study will include AST, ALT, total bilirubin, and alkaline phosphatase.

Nanrilefusp alfa-related hepatic toxicities should be managed as shown in [Table 6.2](#).

Table 6.2: Management of nanrilkefusp alfa-related hepatic toxicities

Nanrilkefusp alfa-related hepatic toxicity	Severity	Nanrilkefusp alfa dose modification
AST increased or ALT increased, or blood bilirubin increased	Grade 2 with AST or ALT >3 to $\leq 5 \times \text{ULN}$ or total bilirubin >1.5 to $\leq 3 \times \text{ULN}$	Withhold nanrilkefusp alfa Resume nanrilkefusp alfa if increased values return to grade ≤ 1
	Grade ≥ 3 with AST or ALT $>5 \times \text{ULN}$ or total bilirubin $>3 \times \text{ULN}$	Withhold nanrilkefusp alfa Resume nanrilkefusp alfa at one dose level below or reduce by 3 $\mu\text{g}/\text{kg}$ if increased values return to grade ≤ 1 Permanently discontinue nanrilkefusp alfa on second occurrence of grade ≥ 3 hepatic event

Please also refer to the IB, section 6.6 (Management guidelines for identified and potential risks).

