9.3.3.2 Safety endpoints

- DLTs

The incidence of DLTs (in DLT-evaluable patients, see section 4.1.3) by dose level will be summarized with counts and percentages.

- TEAEs

A TEAE is defined as an AE that started or worsened at or after the start of study treatment.

TEAEs will be summarized with counts and percentages. These will be provided for the incidence of, but not limited to: any TEAE, any serious TEAE, any grade 3-5 TEAE, any drug-related TEAE, any serious and drug-related TEAE, any grade 3-5 and drug-related TEAE, temporarily discontinued due to a TEAE, permanently discontinued due to a TEAE, death. TEAE incidence frequencies by system organ class and preferred term will also be provided.

- Safety laboratory findings and vital signs

Safety laboratory findings and vital signs measurements will be summarized accordingly (if categorical or continuous data). Laboratory results will be summarized using SI units as appropriate.

Further details on analyses to be performed will be specified in the final statistical analysis plan (SAP).

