9.5 Sample size determination

In the safety cohorts, the traditional 3+3 design dose escalation will be applied. Therefore, 3 to 6 DLT-evaluable patients per dose level will be included in a cohort. The estimated number of patients is 6-12.

The overall sample determined in this trial is 52 patients in efficacy population (see section 9.2.3) which includes patients from the safety cohorts and the main cohort.

The total sample size is based on a Bayesian calculation: Markov chain Monte Carlo has been used for the sample size determination. Assuming a desired ORR for the number of responses, and a uniform prior distribution between 0 and 1, the sample size of 52 patients will ensure at least 80% posterior probability to achieve an effect above the minimal ORR:

- Benchmark ORR: 20%²¹
- Minimal ORR (relative increase, absolute increase): 28.8% (1.44, 8.8%)
- Desired ORR (relative increase, absolute increase): 36.8% (1.84, 16.8%)

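### The replacement floor stays at 3 patients after a safety cohort is expanded, so 6 evaluable patients are not secured, and patients replaced for a toxicity-related missed dose are not visible in either DLT table

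*Protocol*

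**What the plan says.** **Expansion.** Under protocol 4.1.1, one or more DLTs in the first 3 patients of a safety cohort lead to 3 more being recruited into that cohort. The internal safety committee (ISC) then reviews their safety data and chooses how to proceed. The text counts recruited patients, not evaluable ones.

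**Replacement.** The same section deals with patients who are not DLT-evaluable. Its rule reads: "for any reason other than DLT during the DLT assessment period will be replaced until at least 3 patients per cohort". The floor counts those who got through the 21-day cycle. No other floor is given for an expanded cohort.

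**Evaluability.** Protocol 4.1.3 requires completion of the 21-day cycle and two dosing conditions, each with a 1-day window: "Patient received all administrations of nanrilkefusp alfa during the DLT period as per schedule" and "Patient received cetuximab as per schedule".

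**Holds.** Table 6.2 in protocol 6.5.1 withholds nanrilkefusp alfa for related grade 2 AST, ALT or bilirubin increases, with the instruction "Resume nanrilkefusp alfa if increased values return to grade" 1 or lower. It also withholds for grade 3 and above. Under protocol 4.1.2, grade 2 is below the DLT threshold, and a grade 3 AST, ALT or bilirubin increase lasting 5 days or less is exempt.

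**Sample size.** Protocol 9.5 names the traditional 3+3 design and continues: "Therefore, 3 to 6 DLT-evaluable patients per dose level will be included in a cohort". It estimates 6-12 safety-cohort patients. SAP 2.3 repeats this.

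**Denominator.** Protocol 9.3.3.2 specifies "The incidence of DLTs (in DLT-evaluable patients") by dose level. SAP 5.6.2 summarises DLT incidence by dose level in the all-subjects-as-treated (ASaT) population.

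**The concern.** Two things are left open.

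First, a 3+3 design gets its protection at the second stage from seeing 3 further evaluable patients. A floor of 3 for the whole cohort does not secure them. Each added patient who drops out of evaluability and is not replaced is one chance fewer to see a second DLT before the dose goes forward.

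Second, the plan's own hepatic toxicity rule can make a patient non-evaluable. If a related hold below DLT level pushes a cycle 1 dose outside the 1-day window, the patient fails 4.1.3 for a reason other than DLT. While the floor is unmet, that patient is replaced. The protocol's DLT table then omits the patient, and the SAP's table shows the patient as treated without DLT. Neither shows that the drug caused the missed dose. DLTs are the only endpoint listed for the objective of determining the recommended phase 2 dose, so the table written for that objective would not show this information.

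**Working it through.** **The plan's own figure.** Two dose levels with 3 to 6 evaluable patients each give 2 × 3 = 6 and 2 × 6 = 12, the stated 6-12. Also 52 − 6 = 46, the main-cohort size in the schema. The range contains no allowance for replaced patients.

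**Inputs for the floor.**
- Number added on expansion: 3 (protocol 4.1.1).
- q, the DLT rate among evaluable patients: 1/3 (assumption).
- w, the chance that an added patient is non-evaluable and not replaced: 0.1, 0.2 or 0.3 (assumption; the documents give no rate).
- Protocol and SAP state no numeric DLT limit after expansion, so the quantity computed is the chance of seeing no further DLT in the added patients.

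**Step 1: all 3 added patients evaluable.** (1 − q)³ = (2/3)³ = 0.296, or 0.30.

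**Step 2: no replacement among the added 3.** An added patient contributes an observed DLT with probability (1 − w)q, so the chance of none is [1 − (1 − w)/3]³.

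| w | Calculation | Chance of no further DLT |
|---|---|---|
| 0.1 | (1 − 0.300)³ | 0.34 |
| 0.2 | (1 − 0.267)³ | 0.39 |
| 0.3 | (1 − 0.233)³ | 0.45 |

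**Step 3: how often an expanded cohort falls short of 6.** If the first 3 are evaluable, this is 1 − (1 − w)³ = 0.271, 0.488 or 0.657 for w = 0.1, 0.2 or 0.3.

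**Step 4: a different way of fixing the rate.** Hold the DLT probability at 0.3 per treated patient instead. Without replacement the chance of no further DLT is (1 − 0.3)³ = 0.343. With replacement up to 3 evaluable it is [1 − 0.3/(1 − w)]³ = 0.296, 0.244 or 0.187. The direction is the same and the gap is of similar size.

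**The withheld-dose path.** Read in order, the sections give this sequence:
1. Biochemistry is scheduled before the day 8 doses (schedule of activities).
2. A related grade 2 transaminase rise found then leads to a hold under Table 6.2.
3. If recovery comes too late for the 1-day window, 4.1.3 is not met.
4. The event is not a DLT under 4.1.2, so 4.1.1 calls for replacement while the floor is unmet.

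SAP 5.6.2 adds that a patient with a DLT is evaluable whatever doses were given, but adds nothing for this patient.

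**Effect on the tables.** As an illustration, take 4 patients treated at a dose level, 1 replaced for such a hold and 1 DLT among the other 3. Protocol 9.3.3.2 gives 1/3 = 33%, and SAP 5.6.2 gives 1/4 = 25%. Neither figure identifies the fourth patient as someone who missed a dose because of the drug.

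**The case against.** **The floor is only loose wording.** Naming the traditional 3+3, with up to 6 evaluable patients per dose level, suggests that 6 are intended after expansion, and the ISC will look at the added 3. As a statement of intent this is fair. It does not settle the rule: 3 to 6 also admits 4 or 5, the added patients are recruited into the same cohort, and the floor is set per cohort. It is also set in patients who completed the period, which is not the same as evaluable.

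**A reader might quote a larger effect.** If only 1 of the added 3 is evaluable, the chance of no further DLT is 0.67, and if none is, it is 1.00. These cases are uncommon. For w from 0.1 to 0.3, exactly 1 evaluable has probability 0.027 to 0.189, and none has 0.001 to 0.027. The weighted figures in Step 2 are the right measure.

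**A reader might infer that replacement biases the DLT rate towards tolerability.** The documents do not support that. An event below DLT level was never in the numerator, so replacement removes a non-DLT from the denominator. Take a DLT probability of 0.1 and a hold probability of 0.2. No DLT in 3 then has probability (0.7/0.8)³ = 0.670 with replacement and 0.9³ = 0.729 if the patient stays as an evaluable non-DLT, so replacement is the stricter of the two. Only against a rule that counts such holds as events, 0.7³ = 0.343, does it look lenient. Whether to count them is a clinical classification.

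**The ISC sees more than the DLT count.** It reviews the safety data, nothing limits it to evaluable patients, and protocol 4.1.2 lets other significant toxicities be called DLTs. The SAP also plans tables and listings of adverse events leading to temporary discontinuation of nanrilkefusp alfa. This stands and softens the second part. The gap that remains is that those tables are overall rather than per dose level and are not tied to evaluability or replacement.

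**Conclusion.** The point holds in two limited parts.

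First, the written replacement rule does not secure 6 evaluable patients in an expanded cohort. The chance of seeing no further DLT rises from 0.30 to between 0.34 and 0.45. This assumes a DLT rate of 1/3 among evaluable patients and 10% to 30% of added patients non-evaluable and not replaced. The loss is modest, but it falls at the step where a DLT has already occurred.

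Second, a patient replaced after a related hold below DLT level is handled differently by the protocol and the SAP denominators, and neither table shows the reason. The result is lost tolerability information, not by itself a downward bias in the DLT rate. It arises only when the withheld dose falls outside the 1-day window.

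A reader might go further and say that a dose could go forward on 0 of 3 while several treated patients could not complete cycle 1 because of it. That would require the ISC to disregard those patients, and the documents do not say that it does. Table 6.2 and 4.1.3 can both be followed. What is missing is a statement of how the affected patients count.

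**What to change.** - In protocol 4.1.1, state the replacement target in DLT-evaluable patients: 3 before expansion and 6 after it. Align protocol 9.5 and SAP 2.3.
- Use one denominator for DLT incidence in protocol 9.3.3.2 and SAP 5.6.2.
- Give the ISC, and show in the DLT table, per dose level: the number treated, the number DLT-evaluable, the number with related cycle 1 dose omissions, and the number replaced for that reason.
- Reconcile protocol 4.1.1, 4.1.3 and Table 6.2 with SAP 5.6.2 on how a patient with a related hold below DLT level counts. The clinical classification is for the sponsor and the ISC.

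The cost is amendment wording and a few extra rows in one table. Reaching 3 evaluable among the added patients takes on average 3/(1 − w) = 3.33, 3.75 or 4.29 enrolled for w = 0.1, 0.2 or 0.3. That is possibly one or two more replacement patients in an expanded cohort.

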4.1.2 DLT definition

For the safety cohorts, DLTs will be AEs listed below, specified and graded according to CTCAE, version 5.0, without consideration of causality to nanrilefusp alfa. AEs listed below will be considered DLTs unless clearly not related to nanrilefusp alfa (i.e., events clearly due to cancer, other comorbid illness, or unequivocally related to concomitant medications).

Every DLT in the study will be discussed with the study investigators and every effort will be made to ensure all clinical assessments are carried out and documented appropriately and, wherever possible, histological assessments are also performed to identify and understand the safety profile of nanrilefusp alfa in combination with cetuximab.

AEs that are considered DLTs

- All grade 5 events not clearly related to disease progression or any other causes will be considered DLTs.
- Any grade 3 or higher non-hematologic toxicity regardless of duration will be considered a DLT, with the following exceptions that are not considered DLTs:
 - Grade 3 nausea, vomiting, or diarrhea that can be controlled within 72 hours
 - Grade 3 fatigue that lasts less than 5 days
 - Grade 3 or higher correctable electrolyte abnormalities that last less than 72 hours and are not associated with clinical complications
 - Grade 3 or higher serum amylase or lipase not associated with clinical manifestations of pancreatitis
 - Grade 3 aspartate aminotransferase (AST) or alanine aminotransferase (ALT) increase or grade 3 blood bilirubin increase that lasts 5 days or less
- Hy's law cases will be considered DLTs (see section [10.3](#)).
- Hematologic DLTs will include the following:
 - Grade 4 decreased neutrophil count or decreased platelet count lasting more than 7 days
 - Febrile neutropenia
 - Grade 3 or higher decreased platelet count with bleeding

AEs that are not considered DLTs

- Inflammatory reaction attributed to a local antitumor response (grade 3 tumor pain caused by acute inflammatory reaction at tumor-bearing sites, e.g., like sites of metastatic disease or lymph nodes) that resolves to grade 1 within 3 weeks
- Concurrent vitiligo or alopecia of any CTCAE grade

Other clinically significant toxicities, including a single event or multiple occurrences of the same event, may be considered DLTs in the safety cohorts.

